## **Tool Revision History**

Version Number 3:

version Date: 10/26/2017 Summary of Revision Made:

Added a +/-2min window for collection of the q10 min data on the dental chair to avoid protocol violation in case the dental procedure results in expected or realized delay of sampling

Version Number: 2 Version Date: 9/8/2017

Summary of Revisions Made:

More detail and validation provided for scales used Approach to intermittent missing data inserted

Version Number: 1 Version Date: 8/31/2017 Summary of Revisions Made:

## **PRÉCIS**

#### **Study Title**

Nonpharmacologic reduction of periprocedural pain, anxiety, and prescription drug use

#### **Objectives**

Objectives of this Phase I pilot trial are to provide data towards assessing and facilitating feasibility of a larger scale Phase II trial in which the effects of a calmative Comfort Talk® app can be unequivocally evaluated.

Towards this goal we will pursue following outcome parameters for

Phase I: Feasibility/acceptability assessment:

Primary outcome parameter:

• ability to obtain complete on-site data sets from at least 90% of patients enrolled (with at least 40% from patients in the app group and at least 40% from patients in the control group).

Secondary outcome parameters:

- ability to enroll 60 patients by day 150 after initiation of recruitment in the clinic (=day 1)
- •
- Obtain 38 packages of filled out diary cards (at least 16 from patients in the app group and at least 16 from patients in the control group)

• 90% of patients in app group listen to app  $\geq$ 5 min

### Phase II preparation

primary outcome parameter

• anxiety at the end of the waiting room time

#### Secondary outcome parameters

- pain the end of the waiting room time
- anxiety during treatment
- pain during treatment
- anxiety during 1 week after treatment
- pain during 1 week after treatment
- use of units of sedatives and analgesics during 1 week after treatment
- patient satisfaction

## **Design and Outcomes**

The design is a single-blind, placebo controlled clinical trial to test the feasibility of the trial design assessing the ability of a Comfort Talk® app to nonpharmacologically reduce anxiety, pain, and periprocedural drug use in individuals 18 years of age and older undergoing outpatient treatment in the Craniofacial Pain Center of the Tufts School of Dental Medicine.

The trial is a single-site pilot trial to assist in sample size estimation in a pivotal trial to test the hypothesis that listening to a Comfort Talk® app with calmative content reduces pain, anxiety, and post-procedural medication use.

Eligible patients at the Craniofacial Pain Center at the Tufts School of Dental Medicine (TUSDM) will be randomized to listen to a tablet containing a calmative Comfort Talk® app or app with white noise on an intent-to-treat basis. Their anxiety and pain measures will be recorded on validated 0-10 scales and before listening, at the end of the waiting room period, and every 10 minutes (+/- 2 minutes) while on the dental chair.

All patients will be given a packet with diary cards to record their levels of anxiety, pain, and drug use daily for 7 days after their visit and asked to send those back. Subjects will be mailed a \$25 check upon returning their diaries.

Patients randomized to the Comfort Talk® app will receive a download coupon for the app before leaving TUSDM, those randomized to the control condition (white noise) will receive a download coupon after they send in their diary cards.

#### **Interventions and Duration**

Approximately 1 hour and 15 minutes (Up to 30 minutes more than the scheduled standard of care visit, which will typically last up to 45 minutes):

Patient will be asked to come in ½ hour early before an already scheduled appointment. They will be taken to a private area, report their demographics, and if eligible consented and fill out a NIDA Quick Screen.

The participant will then be verbally asked to indicate his/her pain and anxiety levels on validated 0-10 scales. The research assistant will then hand the participant a tablet containing, depending on the group attribution, either the app (App Group) or white noise (Control Group) and will be shown how to operate the tablet.

Participant will then return to the clinic waiting area with the tablet and wait for their regularly scheduled appointment. The patient will be at liberty to when and for how long to listen. At the end of the waiting room period the participant will be queried again for their levels of pain and anxiety.

After the participant enters the treatment room, he or she will be able to continue to listen to the app or white noise on the tablet. The research assistant will ask the participant every 10 min (+/- 2 minutes) to indicate their pain and anxiety levels. The research assistant will note the duration of chair time, the amount of lidocaine given, if any or which other medications were given during the appointment, and whether the dental practitioner prescribed opioid, prescription or non-prescription drugs at the end of the visit.

Before leaving home, the participant will be asked to fill out a satisfaction survey based on a modified Press Ganey Template. The participant will then receive a diary card on which to note pain, average and maximal pain as well its location, use of non-prescription, prescription, and opiate drugs, use of the app, and be provided prestamped envelopes. Patients will be asked to complete the diary daily before bedtime for 7 days.

#### Sample Size and Population

The pilot will be conducted in the Craniofacial Pain Center of TUSDM. Patients included in the trial will be those who come for the procedures offered in the Craniofacial Pain Center such as fitting and adjusting dental bite appliances, fitting and adjusting oral appliances for management of sleep apnea, trigger point therapy, botulinum toxin therapy, and various craniofacial and cervical nerve blocks for pain management. Procedures last on the average 45 min.

Subjects will be randomized to one of four tablets using a randomization plan generated by SAS version 9.4 PROC PLAN. Given that four tablets will be available at one time, four subjects will be randomized per block. Given a total sample size of 72, subjects will be randomized to 18 blocks.

#### 1. STUDY OBJECTIVES

## 1.1 Primary Objective

The primary objective concerns feasibility/acceptability of the trial design. This will be assessed by the ability to obtain complete on-site data sets from at least 90% of patients enrolled (with at least 40% from patients in the app group and at least 40% from patients in the control group).

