## 1.2 Secondary Objectives

Secondary objectives further assess overall feasibility of the trial design and aim to obtain sufficient data to assess the ability to calculate reliable sample size requirements for Phase II.

Feasibility parameters:

- ability to enroll 60 patients by day 150 after initiation of recruitment in the clinic (=day 1)
- Obtain 38 packages of filled out diary cards. (at least 16 from patients in the app group and at least 16 from patients in the control group)
- 90% of patients in app group listen to app  $\geq 5$  min

Since a significant reduction in anxiety in the waiting room is the main ingredient that underlies all other hypothesized effects for Phase II outcomes, even in the face of proven technical feasibility of trial execution, it was also taken into consideration for sample size calculations.

We hypothesize that use of the active Comfort Talk® app results in a reduction in anxiety by 35% at the end of the waiting room time. This degree of reduction in anxiety is clinically significant based on prior work in a clinical trial that demonstrated that a 35% difference in anxiety at the onset of an invasive medical procedure is associated with significant differences in the subsequent experience of pain and anxiety during the procedure, need for opioid analgesics and sedatives, and the overall length of the procedure (1). These factors directly affect procedure safety and throughput (e.g. economical efficiency).

Secondary clinical outcome parameters will be:

- anxiety at the end of the waiting room time
- pain the end of the waiting room time
- anxiety during treatment
- pain during treatment
- anxiety during 1 week after treatment
- pain during 1 week after treatment
- use of units of sedatives and analgesics during 1 week after treatment
- patient satisfaction

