#### 3. STUDY DESIGN

- 1. This is a single-blind placebo controlled trial comparing a Comfort Talk® calmative app (App Group) with a white noise app (Control Group).
- 2. Primary outcome parameter will be ability to obtain complete on-site data sets from at least 90% of patients enrolled (with at least 40% from patients in the app group and at least 40% from patients in the control group).

Secondary Feasibility parameters will be:

- ability to enroll 60 patients by day 150 after initiation of recruitment in the clinic
   (=day 1)
- obtaining 38 packages of filled out diary cards (at least 16 from patients in the app group and at least 16 from patients in the control group)
- 90% of patients in app group listen to app  $\geq 5$  min

Phase II outcome parameters:

Primary: anxiety at the end of the waiting room time.

Secondary:

- pain the end of the waiting room time
- anxiety during treatment
- pain during treatment
- anxiety during 1 week after treatment
- pain during 1 week after treatment
- use of units of sedatives and analgesics during 1 week after treatment
- patient satisfaction
- 3. Study population: 72 eligible patients (36 test group, 36 control group)

- 4. Study location: Outpatient clinic at TUSDM
- 5. Enrollment period and follow-up time:
  - For individual patients: time of clinic visit data collection on site plus 7 days at home follow-up by diary card
  - For the entire trial: 6 months
- 6. Description of intervention: The research assistant will hand the participant a tablet containing, depending on the group attribution, either the app (App Group) or white noise (Control Group) and will be shown how to operate the tablet.

Participant will then return to the clinic waiting area with the tablet and wait for their regularly scheduled appointment. The patient will be at liberty to when and for how long to listen.

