Using this number of 66 patients as guide to determine a target study size for assessment of the feasibility parameters an enrollment of 72 patients seemed compatible with an early drop-out of 6 patients resulting in an expected 91.7% onsite data return rate. This will also support the expectation of receiving 38 packages of filled out diary cards (53%), a secondary objective. In a prior breast biopsy trial, in which patients collected for 5 days 4 daily salivary cortisol samples, filled out more extensive diary cards, and sent all back to the lab, 36% complied (45). Considering the higher burden of also getting 4 daily salivary samples and 4 daily entries as compared to one daily entry on cards at bed-time a 53% return rate for this pilot is reasonable.

This sample size of 72 participants may also give an estimate in as far results previously achieved with live delivery of Comfort Talk® may be transferable to assumptions for app delivered Comfort Talk® content.

The following sample size estimate supports the evaluation of post-procedure pain and is based on a prior breast biopsy trial (19) during which we collected postoperative pain measures. In that study, postoperative pain ratings in the live Comfort Talk group were less than those of the control group (1.6 vs 3.5) with a standard deviation of 2.0. Assuming a similar reduction in pain from 3.5 to 1.6 on day 1 (similar effect size in a study by from TUSDM) (43) and a standard deviation of 2.0, 38 subjects total would be needed for a two-sided test with a power of 0.80 and an alpha of 0.05. Considering that not everyone will send back their diaries, the target of 72 patients may suffice.

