#### 9.5 Outcomes

The outcomes are based on patient's reported measures of anxiety, pain, satisfaction rating on a Likert scale, and medication use and objective numbers with regard to the feasibility measures. These data are clear numerical values and not subject to interpretation/adjudication with regard to their reported value.

There will be no loss of follow-up for data for the primary outcome parameter since all patients who are on site are the denominator and any missing data would be reflected in the percentage of complete on-site data sets.

For management of any subsequent missing intermittent data the method will use all data available data that are available within the intent-to-treat overall approach.

We will be using all available data and calculate the percent missing data for each treatment group. The degree of missingness will inform accept/reject feasibility which is defined as complete on-site data sets from at least 90% of patients enrolled with at least 40% from patients in the app group and at least 40% from patients in the control group) and 38 packages of filled out diary cards 52% with at least 16 (22%) from patients in the app group and at least 16 from patients in the control group (22%)

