## 9.6 Data Analyses

All outcome parameters for assessment of study feasibility are pass/fail criteria not requiring further analyses beyond calculations of sums and percentages.

To commit to a detailed analyses in Phase II, this can only be done with the proviso that the approach may change based on the data distribution, central measures and variation, and particularly time course, the determination of which is a goal of this Phase I trial.

For comparison of change in anxiety and pain from start to end of the waiting room time we propose t-test if normally distributed or the Mann-Whitney U test in the case of non-normal data.

For the time course assessment of pain and anxiety during the procedure there are options depending on whether the data meet the assumptions required for time course analysis.

Descriptive statistics (means and standard deviations as well as counts and percentages) will be calculated for each outcome stratified by time point and by

treatment group. Pain and anxiety trends over time will be assessed graphically for each patient stratified by treatment group.

With the provision that the analysis plan will be adapted based on the metrics found in Phase I, the plan is to follow a previously described path (24):

If the relationship between pain/anxiety is linear over time, and if needed, normality and homoscedasticity of residuals can be achieved by log-transformation, a repeated-measures analysis to compare the effect of treatment, time, and treatment by time interaction on pain and anxiety responses to characterize and compare trends in pain and anxiety ratings for the two treatment conditions over time (66, 67). The analysis will use the reports from the successive 10 min (+/- 2 mins) intervals queries obtained from all patients.

It may be that residuals are neither normally distributed nor possible to obtain a normal distribution by transformation. This happened in prior large scale trial with procedural pain procedural were 47% of pain responses were zero (45). To accommodate such a strong skew in reported pain, we would change our statistical approach to ordinal regression (68). If the proportional odds assumption is met, ordinal regression accounting for repeated measures will be performed to compare the effect of treatment, time, and interaction of treatment by time on pain and anxiety responses. The results will be presented in terms of the slopes of the time course of pain and anxiety on the logit scale.

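### Does the per-arm 40% clause of the primary feasibility criterion need changing, given that the overall 90% rule already implies it?

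*Combined protocol and SAP*

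**What the plan says.** Section 1.1 sets an overall threshold of 90% of enrolled patients with complete on-site data, "with at least 40% from patients in the app group and at least 40% from patients in the control group". The Précis and sections 3, 9.1 and 9.5 repeat it. None of them says what the 40% is a percentage of. The nearest guide is the diary criterion in section 9.5, "38 packages of filled out diary cards 52% with at least 16 (22%) from patients in the app group": 16/72 is 22%, whereas 16/36 would be 44%, so that percentage is taken on all enrolled patients. Section 6.2.5 also makes total enrolment the denominator.

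Section 3 plans "72 eligible patients (36 test group, 36 control group", and the Précis describes the blocking: "four subjects will be randomized per block. Given a total sample size of 72, subjects will be randomized to 18 blocks". Two of the four tablets carry the app and two carry white noise, so every full block is split 2:2.

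On how the criterion is used, section 9.6 says: "All outcome parameters for assessment of study feasibility are pass/fail criteria not requiring further analyses beyond calculations of sums and percentages". Section 9.5 adds that the statisticians will "calculate the percent missing data for each treatment group. The degree of missingness will inform accept/reject feasibility". Section 9.2 expects an "early drop-out of 6 patients resulting in an expected 91.7% onsite data return rate".

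**The concern.** The wording suggests two tests, one on the trial as a whole and one on each arm. If the per-arm test can never fail once the overall test has passed, a pass tells the reader nothing extra about the arms. Differential loss is the kind of problem a per-arm test should catch. Sections 2.2 and 7.1 foresee that anxious control patients may be disappointed at not getting the app, and the pilot data are meant to guide the sample size and analysis of Phase II. One arm could be fully complete and the other 19.4% incomplete, and the primary criterion would still be met.

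The diary criterion has the same form, "at least 16 from patients in the app group and at least 16 from patients in the control group", and there the floor does change verdicts. That contrast makes the on-site clause look like an oversight.

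**Working it through.** **Inputs.** N = 72 in two arms of 36 (section 3); overall threshold 90% and per-arm figure 40% (section 1.1); 6 early drop-outs (section 9.2); diary target 38 with at least 16 per arm (section 1.2).

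**The plan's own figure.** (72 − 6)/72 = 66/72 = 91.7%. It reproduces.

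**What the 90% rule forces.** 0.90 × 72 = 64.8, so at least 65 sets are needed (65/72 = 90.3% passes; 64/72 = 88.9% fails). One arm supplies at most 36, so the other supplies at least 65 − 36 = 29.

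**The clause under each possible base.**

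| Base for the 40% | Lowest value among outcomes meeting 90% | Clause met? |
|---|---|---|
| All enrolled | 29/72 = 40.3% | yes |
| Own arm | 29/36 = 80.6% | yes |
| All complete sets | 29/65 = 44.6% | yes |

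A total T between 65 and 72 can arise in 72 − T + 1 ways, so the number of passing pairs is 8 + 7 + … + 1 = 36. The clause rejects none of them on any base. The widest gap that passes is 36/36 against 29/36, or 19.4 percentage points.

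**In general.** With equal arms of N/2 and a total of at least 0.9N, each arm supplies at least 0.9N − 0.5N = 0.4N. The 40% is that minimum.

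**Where the clause can act.** If enrolment stops mid-block, the arms can differ by 1 or 2. For N from 60 to 80, nine such splits each have exactly one count pair that meets 90% and fails the clause, and only on the enrolled base. At 36:35, for example, 36 + 28 = 64 of 71 is 90.1%, while 28/71 is 39.4%.

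**Diary comparison.** The 38 packages force only 38 − 36 = 2 from the smaller arm. Of the 630 count pairs reaching 38, the floor of 16 rejects 210. As a share of the overall target the two floors are close: 16/38 = 42% for the diary and 40/90 = 44% on site. The diary floor acts because its overall target is low (38/72 = 53%).

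**What a stricter floor would do.** Take 85% of each arm as an example: 0.85 × 36 = 30.6, so 31. It rejects 6 of the 36 passing pairs (36+29, 36+30, 35+30 and their mirrors). Pass probabilities are exact sums over two independent Binomial(36, p) counts:

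| Completion, arm 1 / arm 2 | 90% rule as written | With 31/36 floor |
|---|---|---|
| 91.7% / 91.7% (plan) | 75.0% | 73.1% |
| 95% / 95% (assumed) | 97.3% | 96.6% |
| 98% / 85% (assumed) | 73.7% | 53.3% |
| 100% / 81% (assumed) | 62.6% | 29.6% |

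**The case for a change.** The best argument for a change is that this is the trial's primary outcome, stated in five places, and one of its two parts decides nothing at the planned allocation. The diary floor suggests that the sponsor wants per-arm checks that act. Adding one here needs only wording, and under a marked imbalance it would separate good from poor results: at assumed completion of 100% and 81%, the pass probability would fall from 62.6% to 29.6%.

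The arithmetic behind this stands. The inference that something must be repaired is weaker. The documents never say that the clause was meant to be stricter than the 90% rule, and as a statement of what each arm must contribute it is exact. The unequal rates that make a stricter floor look useful appear nowhere in the documents. Section 9.2 allows that completion may be lower than in the earlier live-delivery trials, but predicts no difference between arms. If the arms complete equally, every verdict that the stricter floor changes is a failure caused by chance imbalance. The diary contrast comes from the lower overall target, since the two balance shares are nearly the same.

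**Conclusion.** The clause is redundant at 36:36 and changes 0 of the 36 passing outcomes. No figure in the plan is wrong, and the sections that state the criterion agree with one another. The 90% rule already holds each arm to at least 29/36 (80.6%), and section 9.5 has missingness calculated by group, so anyone planning Phase II would see a gap between that limit and 100%. For a pilot judged on practical pass/fail criteria, that is sufficient.

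Neither possible edit earns its place. Deleting the clause alters no verdict at the planned allocation and would remove its small role when enrolment ends mid-block. Setting a higher own-arm floor is a fresh design choice. Its level would be a matter of judgement, and an 85% floor would cost about 2 percentage points of pass probability at 91.7% completion (75.0% to 73.1%) and 0.6 at 95% (97.3% to 96.6% before rounding). Statisticians could reasonably differ on whether that is worth paying.

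The result of no effect rests on equal arms, which 18 full blocks with 2:2 splits deliver, and holds for all three bases of the 40%. The pass probabilities also assume that patients complete independently with a common rate in each arm. When reporting, the analysts can give completeness by arm and note that the 40% condition follows from the 90% rule.

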## 1.2 Secondary Objectives

Secondary objectives further assess overall feasibility of the trial design and aim to obtain sufficient data to assess the ability to calculate reliable sample size requirements for Phase II.

Feasibility parameters:

- ability to enroll 60 patients by day 150 after initiation of recruitment in the clinic (=day 1)
- Obtain 38 packages of filled out diary cards. (at least 16 from patients in the app group and at least 16 from patients in the control group)
- 90% of patients in app group listen to app  $\geq 5$  min

Since a significant reduction in anxiety in the waiting room is the main ingredient that underlies all other hypothesized effects for Phase II outcomes, even in the face of proven technical feasibility of trial execution, it was also taken into consideration for sample size calculations.

We hypothesize that use of the active Comfort Talk® app results in a reduction in anxiety by 35% at the end of the waiting room time. This degree of reduction in anxiety is clinically significant based on prior work in a clinical trial that demonstrated that a 35% difference in anxiety at the onset of an invasive medical procedure is associated with significant differences in the subsequent experience of pain and anxiety during the procedure, need for opioid analgesics and sedatives, and the overall length of the procedure (1). These factors directly affect procedure safety and throughput (e.g. economical efficiency).

Secondary clinical outcome parameters will be:

- anxiety at the end of the waiting room time
- pain the end of the waiting room time
- anxiety during treatment
- pain during treatment
- anxiety during 1 week after treatment
- pain during 1 week after treatment
- use of units of sedatives and analgesics during 1 week after treatment
- patient satisfaction

